## (3) Assessment of antigen-spread to other prostate-associated antigens

High-throughput immunoblot (HTI): An exploratory objective of the study will be to determine if patients treated develop “off-target” prostate cancer antigen-specific immune responses as evidence of antigen spread. Future studies may evaluate T-cell responses to non-targeted antigens. However, the primary evaluation will be to evaluate IgG responses to a panel of prostate-associated antigens as we have previously reported in patients treated with vaccines or other immune-

modulating agents [68-70]. IgG specific for 126 antigens, including 29 cancer-testis antigens [71, 72] and 97 prostate antigens frequently immunologically recognized [73-76] will be identified by screening a high-density phage array expressing these individual antigens, as we have previously reported [68, 70, 71]. An alternative to this approach may include the evaluation of responses to panels of protein or peptide antigens fixed to support membranes provided by commercial vendors. The primary analysis will be conducted using sera obtained at 6 months, and compared with IgG responses identified at baseline, to determine whether IgG specific for individual antigens are elicited over time. Other time points will be assessed to determine the durability and kinetics of immune response development, and confirmatory ELISA studies will be performed where feasible.

**REPORTING AND RESPONSE DEFINITION:** A positive IgG response will be defined as an immunoreactive spot to a defined antigen, scored by at least 3 of 4 independent reviewers, and detectable to at least 2 of 3 replicates per immunoblot membrane as previously described [68, 77], or by statistically defined criteria using commercial antigen sources. An IgG response resulting from immunization will be defined as an immunoreactive antigen identified at the 6-month (or other post-treatment time for subsequent analyses) time point that was not identified at the pre-treatment time point.

#### C. Serum PSA Doubling Time Evaluation

See Section 11 for further details. Serum PSA doubling-time (or PSA slope) response will be considered a secondary endpoint. The pre-treatment serum PSA doubling time will be calculated from four serum PSA values available from the same clinical laboratory using the same assay for the period up to one year prior to study treatment, not on other treatments for prostate cancer, up to and including the PSA value obtained at screening, using the Memorial Sloan-Kettering Cancer Center nomogram

(<http://www.mskcc.org/applications/nomograms/prostate/PsaDoublingTime.aspx>). The post-treatment PSA doubling time will be calculated using the same nomogram from:

- (1) All PSA values obtained from the same clinical laboratory using the same PSA assay beginning with the PSA value at day 1 (week 0) and continuing until the end-of study (or month 24) value (PSADT0-24).
- (2) All PSA values obtained from the same clinical laboratory using the same PSA assay beginning with the PSA value at week 12 (month 3) to the week 36 (month 9) value (PSADT3-9).

An increase in the PSA doubling time to at least double the baseline value, and at least 15 months, will be considered a PSA doubling time “response” [7].

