#### B. Secondary Objectives

1. To evaluate 2-year metastasis-free survival rate
2. To evaluate median radiographic progression-free survival
3. To evaluate changes in PSA doubling time or slope
4. To evaluate PSA response rate ( $\leq 50\%$  of baseline)
5. To determine whether GM-CSF is required as a vaccine adjuvant for pTVG-HP vaccine when used in combination with nivolumab

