#### B. Endpoints

The primary endpoints for the trial will be safety, tolerability, and PSA complete response (PSA CR) rate. A PSA CR will be defined as a serum PSA <0.2 ng/mL, with a confirmatory PSA <0.2 ng/mL at least 4 weeks later, as per PCWG2 recommendations [67]. To qualify as a PSA CR, there must be no evidence of radiographic progression. Patients will come off study at the time of appearance of metastatic disease (radiographic progression), at the time of undue toxicity (as defined below), or at the discretion of the patient and treating physician that other therapies for

prostate cancer are warranted. Patients should be discouraged from discontinuing protocol treatment for PSA rise only. Patients will continue to have blood drawn for immune studies, as per study calendar, up to one year after screening, even if off study prior to that time.

All subjects will undergo radiographic imaging (CT of abdomen and pelvis and bone scan) prior to treatment, and at 6-month intervals (or as clinically indicated). The appearance of lesions consistent with metastatic disease will be used to define radiographic progression, and from these the 2-year metastatic progression-free survival will be calculated for each treatment arm, as well as the median progression-free survival. NOTE: Lesions detected by F-NaF-PET/CT or other advanced imaging (such as NaF-PET/CT, choline PET/CT, fluviclovine, or PSMA PET scans) only will not be used to define metastatic disease or disease progression. MRI imaging may substitute for CT, but the same type of imaging must be used to determine eligibility and progression. RECIST 1.1 criteria will be used to define metastatic disease (appearance of a visceral lesion > 10 mm by CT or MRI, lymph node > 15 mm in short axis, or appearance of new lesions on bone scan consistent with metastatic disease). The 2-year metastasis-free survival will be determined by investigator review of radiographic studies (CT/MRI and bone scintigraphy) performed 2 years after study initiation in subjects who have not already met criteria for radiographic progression.

PSA doubling times will be calculated from four available serum PSA values obtained up to one year from the same clinical laboratory prior to study enrollment, up to and including the baseline value, and used to determine a pre-treatment PSA doubling time (PSADT). Similarly, a post-treatment doubling time will be calculated from:

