R. Week 84 visit (84 +/- 14 days after week 72 visit)

1. Physical examination, including vital signs, symptoms assessment, and ECOG performance score
2. Blood draw CBC, chemistry panel, PSA and PAP.

S. Week 96 visit (84 +/- 14 days after week 72 visit) – END OF STUDY

1. Physical examination, including vital signs, symptoms assessment, and ECOG performance score
2. Blood draw CBC, chemistry panel, PSA and PAP.
3. CT scan of abdomen and pelvis, and bone scan (can be performed +/- 7 days of this visit)

T. 28-Day Follow Up Visit (28 +/- 7 days after Off-study date, if prior to week 48)

Patients will come off study at the time of disease progression, undue toxicity, or at the discretion of the patient and/or treating physician that it is not in the interest of the patient to continue treatment. A separate follow-up visit is not required for patients completing the week 48 evaluation, however for patients coming off study prior to week 48, 28-day follow up visit will include the following:

1. Physical examination, symptoms assessment, and ECOG performance score.
2. Blood draw for CBC, chemistry panel, serum PSA and PAP
3. IF NOT ALREADY COLLECTED WITHIN PREVIOUS 60 DAYS: 10 ml peripheral blood (red-top tubes) for sera to evaluate antibody responses, and 100 ml peripheral blood (green-top heparinized tubes) for T-cell response evaluation

U. Long-term Follow-Up

Subjects will be contacted by telephone (if not already being seen in clinic) annually for 2 years following the last DNA vaccination to collect clinical information to identify any potential long-term risks. This information has been requested by FDA for all gene delivery trials to assess potential long-term risks. The specific information to be collected annually will include:

- Date of contact
- Current medications
- Hospitalizations (dates and reasons for hospital admission)

- Stage of prostate cancer, treatments for prostate cancer, and recent serum PSA level
- New cancer diagnoses
- New autoimmune disorders
- New hematologic or neurologic disorders
- Other new medical diagnoses
- Date of death if patient deceased

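### PSA response and the post-treatment PSA doubling times have no cut-off at the start of other prostate cancer therapy, so a PSA drawn after early exit can score a failure as a response

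*Combined protocol and SAP*

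**What the plan says.** Section 9.C defines two post-treatment doubling times. PSADT0-24 uses "All PSA values obtained from the same clinical laboratory using the same PSA assay beginning with the PSA value at day 1 (week 0"), "continuing until the end-of study (or month 24) value". PSADT3-9 uses the same kind of values from week 12 to week 36. Section 6.B gives the same two rules. The only limits are laboratory, assay and window. The pre-treatment doubling time in 9.C carries one more: its values must come from a period without other prostate cancer treatment. A doubling-time response is at least twice the baseline value and at least 15 months.

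The relevant secondary objective in Section 3.B reads "To evaluate PSA response rate", with the threshold at or below 50% of baseline. No confirmation, time window or therapy cut-off is given, and Section 10.D(3) has no paragraph on this endpoint. The primary endpoint, PSA complete response, needs a second value below 0.2 ng/mL at least 4 weeks later and no radiographic progression (Section 6.B).

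Under Section 6.B patients may come off study "at the discretion of the patient and treating physician that other therapies for" prostate cancer are warranted. Section 8.T then schedules a visit "28 +/- 7 days after Off-study date, if prior to week 48", which includes "Blood draw for CBC, chemistry panel, serum PSA and PAP". Section 8.S attaches the end-of-study label to the week 96 visit: "84 +/- 14 days after week 72 visit) – END OF STUDY".

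**The concern.** The protocol guards the baseline side of a before-and-after comparison against PSA values altered by other treatment, but not the follow-up side. The last scheduled PSA for an early leaver comes 21 to 35 days after the off-study date, and one recognised reason for leaving is that another therapy is wanted. Section 1 says that men at this stage are often treated with androgen deprivation. Nothing written keeps a PSA lowered by the new therapy out of PSADT3-9, PSA response or, depending on how its end-point is read, PSADT0-24.

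The error runs one way: it credits the study treatment with another treatment's effect, and a single-arm trial has no control group in which it could cancel. It also spreads. PSA response is the outcome in the Section 10.D(4) logistic regressions on T-cell response and antigen spread, and doubling times before and after treatment are compared by a paired test in 10.D(3).

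**Working it through.** **The plan's own figure.** The documents give none for this point. The primary design does reproduce: stopping at 1 or fewer of 21 and rejecting at 5 or more of 41 gives exact power 0.902 at a true rate of 20%, against the stated 90%. The step below does not change that design.

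**Inputs from the documents.** PSADT = ln 2 / slope of log PSA on time (10.D(3)). PSA every 4 weeks from day 1, as listed visit by visit in Section 8. One PSA about 4 weeks after exit (8.T). Response rules as above.

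**Assumptions, not in the documents.** True doubling time 6 months, unchanged by treatment; exit at week 24; new therapy lowers PSA by a fraction d from its week-24 value by week 28. One month is 4.348 weeks, so 4 weeks is 0.920 months.

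**Without the week-28 value.** Slope = 0.6931/6 = 0.1155 per month and PSADT = 6.0 months. Week-24 PSA is 2^(5.52/6) = 1.89 times day 1. The patient is neither kind of responder.

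**With the week-28 value.** That point departs from the patient's own line by ln(1-d) - 0.920 × 0.1155 = ln(1-d) - 0.1063. The slope changes by this departure times (distance of the last time from the mean time) / (sum of squared deviations of time).

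- PSADT0-24, weeks 0 to 28: multiplier 3.220/35.54 = 0.0906. For d = 0.50 the departure is -0.7994, the slope is 0.1155 - 0.0724 = 0.0431, and PSADT = 16.1 months. This is a response.
- PSADT3-9, weeks 12 to 28: multiplier 1.840/8.463 = 0.2174. For d = 0.20 the departure is -0.3294, the slope is 0.1155 - 0.0716 = 0.0439, and PSADT = 15.8 months. This is a response.
- PSA response: for d = 0.75, PSA is 0.25 × 1.89 = 0.47 of day 1. This is a response. The threshold is d = 1 - 0.5/1.89 = 0.74.

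**How the result depends on the assumptions.** PSADT0-24 fitted on the study calendar's PSA visits, whose early weeks differ slightly from Section 8 (for d = 0.50 in the case above, 15.8 rather than 16.1 months):

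| True doubling time | Exit | Fall scored as PSADT0-24 response | Fall scored as PSA response |
|---|---|---|---|
| 12 months | week 24 | 24% to 45% | 64% or more |
| 9 months | week 36 | 52% to 78% | 74% or more |
| 6 months | week 24 | 49% to 69% | 74% or more |
| 3 months | week 24 | 85% to 91% | 86% or more |

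For PSADT3-9 with a 6-month doubling time and exit at week 24, falls of 19% to 34% suffice. Above each PSADT range the slope turns negative, and the response rule does not say how to classify that.

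**Weight of one patient.** 1/41 = 2.4 points on the PSA response rate; 1/21 = 4.8 if the trial stops after stage 1.

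**With a cut-off at the start of other therapy.** The illustrative patient keeps PSADT 6.0 months and a PSA above baseline, and is neither kind of responder.

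**The case against.** Several points against this have force.

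- *PSADT0-24 may already close at exit.* If end of study means each patient's own exit, the 28-day value falls outside that window and the 16.1-month example disappears. The documents do not say so, and they give that label to week 96. This is an ambiguity, not a window without an end. PSADT3-9 and PSA response have no such wording and stay open either way.
- *The primary endpoint.* A reader might infer that the complete-response decision is compromised. It is not, in any material way: a single 28-day draw cannot supply two values below 0.2 ng/mL at least 4 weeks apart. What remains is an on-study value confirmed by one taken after new therapy, which the text does not exclude.
- *Large falls.* A reader might suppose that a 75% fall counts under both rules. In the worked case it gives a PSA response but a negative PSADT, which is unclassified. For fast disease (3-month doubling time) the falls required are very large.
- *Few patients may be affected.* Section 6.B discourages stopping treatment for PSA rise alone, and Section 7 keeps patients on study when vaccine-related toxicity ends all treatment. The same-laboratory rule may also drop some late doubling-time values. These shrink the group without removing it.
- *A PSA before new therapy usually exists.* With draws every 4 weeks for most of the treatment period, an extra draw at exit would add little. This stands, and none is requested.
- *A later SAP is promised* (10.D(1)). It could supply the rule. But the text as written directs that all values be used, and Section 9.C points for detail to Section 11, which is now administrative; the statistical section, 10, is silent. The therapy start date also has to be collected during the trial.

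**Conclusion.** The concern holds for PSADT3-9, for the unconfirmed PSA response and, unless end of study means the individual's exit, for PSADT0-24. Followed literally, the rules can turn a patient who failed and moved to other therapy into a responder, and the error then enters the exploratory regressions on PSA response. The mechanism is shown by arithmetic under assumed doubling times, exit weeks and PSA falls. The size of the bias in this trial cannot be estimated: the documents give no rate of early exit, no rate or timing of new therapy, and no expected fall. A reader might infer that response rates will be substantially inflated; the documents support only that they can be, by 2.4 points of PSA response per affected patient at n=41. The 21/41 design and its decision rule are essentially untouched. This should be corrected, as a matter of secondary and exploratory endpoints.

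**What to change.** 1. In Sections 6.B, 9.C and 10.D, exclude PSA values dated on or after the start of any other prostate cancer therapy from PSA response, from both post-treatment doubling times, and from confirmation of a PSA complete response.
2. State that end of study for PSADT0-24 is the earliest of the off-study date, the start of other prostate cancer therapy, and month 24.
3. Record the start date of any other prostate cancer therapy on the CRF at the 28-day visit. Section 8.U already collects prostate cancer treatments at the annual contact but does not list a start date.

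The cost is a few sentences and one CRF field. Patients who start other therapy contribute slightly fewer PSA points. Sample size, visit schedule and PSA draws stay as they are.

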#### D. Quantitative Total Bone Imaging (QTBI) using NaF PET/CT

An assessment of small volume bone metastatic disease (potentially not detected by standard bone scintigraphy) and tumor growth rates will be conducted using QTBI. Patients selected to participate in the NaF PET/CT part of the study will be assessed at baseline, week 12, and week 24 by NaF PET/CT. Metastatic prostate cancer lesions in bone will first be localized and identified based on functional NaF PET uptake, assisted with the anatomical information

provided by CT scans. Segmentation will be performed using an automatic segmentation method (e.g. a fixed SUV threshold), and adjusted with physician guidance. Scans from different time points will be registered to one another using an articulated registration technique employing a rigid registration of skeletal elements (bones) from CT followed by registration optimization by combining with deformable registration of bones and lesions from NaF PET/CT. The lesions between pre-treatment and follow-up scans will be matched to establish longitudinal correspondence of the lesions. For each patient, comprehensive treatment response metrics will be calculated, consisting of SUVtotal (total disease burden), SUVmax (maximum intensity lesion), SUVmean (average intensity), the number of lesions, and total volume of bone lesions. In addition, imaging response metrics will be calculated for each individual lesion. This methodology will specifically be used to assess the growth rate of bone metastatic disease by evaluating changes from baseline to month 3 and from month 3 to month 6. In terms of logistics, each of the clinical centers has the capacity and expertise to perform NaF PET imaging.

NaF-PET/CT IMAGING PROCEDURES: To ensure uniformity as well as optimal data interpretation, a standardized image acquisition protocol will be utilized and the overall imaging analyses will be conducted centrally under the supervision of [name], PhD (co-investigator) at the University of Wisconsin Image Analysis Core (IMAC) facility, with all analysis blinded to study treatment arm. Please refer to the Standard Operating Procedures (SOP) document for NaF-PET/CT procedures, which will be adhered to at both sites, for details of image acquisition, image analysis, image interpretation, image submission for central review, and other imaging-related details.

## **10. Statistical Considerations**

### **A. Overview**

This will be a single-arm, multiple-institution, two-stage phase II trial designed to evaluate the safety and effect of serial intradermal vaccinations of a DNA vaccine encoding PAP with or without rhGM-CSF, and co-administered with nivolumab, on serum PSA in patients with PSA-recurrent, non-metastatic, non-castrate prostate cancer.

### **B. Objectives**

#### **Primary Objectives:**

1. To evaluate the safety and tolerability of pTVG-HP DNA vaccine and nivolumab in patients with clinical stage D0/M0 prostate cancer
2. To determine the PSA complete response rate (PSA < 0.2 ng/mL)

#### **Secondary Objectives:**

1. To evaluate 2-year metastasis-free survival rate
2. To evaluate median radiographic progression-free survival
3. To evaluate changes in PSA doubling time or slope
4. To evaluate PSA response rate ( $\leq 50\%$  of baseline)
5. To determine whether GM-CSF is required as a vaccine adjuvant for pTVG-HP vaccine when used in combination with nivolumab

### Laboratory/Exploratory Biomarker Objectives:

1. To determine if antigen-specific T-cell and/or IgG responses are elicited with treatment
2. To determine if the development of PAP-specific T-cell immune responses are associated with PSA response (decline  $\geq 50\%$ ) To determine if antigen spread (the development of immune responses to other cancer-associated proteins) is associated with PSA response (decline  $\geq 50\%$ )
3. To determine if antigen spread (the development of immune responses to other cancer-associated proteins) is associated with PSA response (decline  $\geq 50\%$ )
4. To determine if Quantitative Total Bone Imaging (QTBI) by NaF PET/CT can identify bone lesions in this patient population not detected by standard bone scintigraphy
5. To determine whether the presence of lesions detected by NaF PET/CT at baseline is associated with early disease progression (within 1 year) by standard radiographic imaging methods (CT and bone scintigraphy)
6. To determine if growth rates, and changes in growth rates, determined by NaF PET/CT are associated with PSA doubling time and changes in PSA doubling time

### C. Study Design and Sample Size Calculation

The primary efficacy endpoint is the PSA complete response (PSA  $< 0.2$  ng/mL) rate. A confirmed PSA CR will be defined as one in which serum PSA at least 4 weeks later is  $< 0.2$  ng/mL, as per PCWG2 recommendations [67]. In this patient population, the PSA CR rate is expected to be less than 5% with standard care. Hence, the null hypothesis that the PSA complete response rate is at most 5% will be tested against the alternative hypothesis that the rate is greater than 5%. A PSA complete response rate of 20% or more, on the other hand, will be considered sufficient evidence to consider further clinical trial investigation. In order to ensure sufficient accuracy in the estimation of PSA complete response, an adequate number of patients should be enrolled in this study. However, in order to avoid treating patients with a potentially ineffective therapy, a Simon optimal two-stage design with one interim analysis for efficacy will be utilized.

In the first stage, 21 patients will be enrolled and evaluated for PSA response. If a PSA complete response is observed in at most one out of the 21 patients, then study will be terminated after the first stage. Otherwise, an additional 20 patients will be enrolled in the second stage for a total of 41 patients.

Assuming that the number of subjects with a PSA complete response is binomially distributed and using a Simon-optimal two-stage design, this design has a significance of 5% and 90% power for detecting a true success (PSA complete response) probability of 20%. If the true PSA complete response rate is only 5%, the study will be terminated after the first stage with 66% probability. The expected sample size is 27 under this scenario. If, however, the true efficacy response rate is 20%, the study will be terminated early with only 6% probability with an expected sample size of 40 patients. The two-stage procedure has 98% power to detect an efficacy response rate of 25% and 71% power to detect an efficacy response rate of only 15%. The operating characteristic of the proposed balanced two-stage design are summarized in the following table:

**Table 1** *Operating characteristics of the Simon-optimal two-stage design*

True PSA complete response rate	Probability of	Power	Expected
---------------------------------	----------------	-------	----------

	early stop after stage 1		sample size
5%	66%	6%	27
10%	36%	35%	34
15%	16%	71%	38
20%	6%	90%	40
25%	2%	98%	41

A sample size of 21 patients for the first stage and 41 patients in total will be also adequate for estimating toxicity rates with sufficient accuracy. Specifically, toxicity rates will be estimated with a standard error of less than 10% with a sample size of 21 for the first stage and the corresponding 95% confidence intervals will be no wider than 40%. Analogously, with a total sample size of up to 41 patients, toxicity rates will be estimated with a standard error of less than 8% and the corresponding 95% confidence intervals will be no wider than 32%.

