**Table 2: Estimated PSA complete response rates, p-values and confidence intervals**

Number of PSA complete responses	Estimated PSA complete response rate †	p-value	Lower 95% CI bound	Upper 95% CI bound
0	0.0%	1.0000	0.0%	0.0%
1	5.7%	0.6590	0.2%	13.3%
2	5.9%	0.2830	1.7%	20.7%
3	8.5%	0.2120	2.6%	20.8%
4	10.9%	0.1140	3.7%	21.3%
5	13.2%	0.0460	5.1%	22.7%
6	15.4%	0.0140	6.7%	24.8%

7	17.7%	0.0040	8.4%	27.2%
8	20.0%	0.0010	10.1%	29.8%
9	22.3%	0.0000	12.0%	32.5%
10	24.6%	0.0000	13.9%	35.2%

† Estimated using Whitehead's bias-adjustment approach

For example, if at the end of the study, PSA complete response efficacy responses are observed in 5 out of the 41 patients, then the estimated (bias adjusted) response rate is 13.2% with a 95% confidence intervals ranging from 5.1% to 22.7%.

A minimum of 5 complete PSA responses are required to reject the null hypothesis which warrants further clinical investigation.

*Toxicity and adverse events:* Subjects will be evaluated at each visit by a review of systems based on the most recent version of the NCI common toxicity criteria. Toxicities will be summarized by type and severity in tabular format. Toxicity rates (grade 2, grade 3, grade 4, grade  $\geq$  2, grade  $\geq$  3, etc.) will be calculated and reported along the corresponding 95% confidence intervals. The 95% confidence intervals will be constructed using the Wilson score method.

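### At the 5% null rate, the plan's early-stopping and rejection probabilities are wrong: 72% (not 66%) and 5% (not 6%)

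*Combined protocol and SAP*

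**What the plan says.** The design is in Section 10.C (Study Design and Sample Size Calculation). The plan says that "the null hypothesis that the PSA complete response rate is at most 5% will be tested". The test is one-sided, with any rate above 5% as the alternative. On the rate that would justify more work, the plan says: "A PSA complete response rate of 20% or more, on the other hand, will be considered sufficient evidence". Stage 1 enrols 21 patients and the trial stops if at most one has a PSA complete response. Otherwise 20 more are enrolled, for 41 in total. The final threshold is in Section 10.D(2), below Table 2: "A minimum of 5 complete PSA responses are required to reject the null hypothesis". The stated significance is 5% and the stated power at 20% is 90%, with a binomial count assumed.

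For a true rate of 5%, the text of Section 10.C says: "If the true PSA complete response rate is only 5%, the study will be terminated after the first stage with 66% probability". The next sentence reads: "The expected sample size is 27 under this scenario". The 5% row of Table 1 gives 66% early stopping, 6% in the power column and an expected sample size of 27.

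Two other statements in Section 10.C are relevant. On power at a higher rate: "The two-stage procedure has 98% power to detect an efficacy response rate of 25" per cent. On toxicity: "toxicity rates will be estimated with a standard error of less than 10% with a sample size of 21 for the first stage".

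**The concern.** Once the stopping bound, the rejection threshold and the two stage sizes are fixed, the 5% row of Table 1 has a single correct answer. The printed row does not fit the rest of the plan. A 6% rejection probability under the null exceeds the stated 5% significance. A 66% stopping probability does not lead to an expected sample size of 27.

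These two figures describe the design's protection against an inactive regimen: how often it stops early and how often it gives a false positive. An ethics committee, the DSMC or a journal reader would take from Table 1 that the trial exceeds its own significance level and stops an inactive treatment less often than it does. Section 10.D(1) says that a detailed SAP will be written later, so the wrong figures could be carried into it.

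**Working it through.** **Inputs.** From Section 10.C: n1 = 21, stop if X1 ≤ 1, second-stage size n2 = 20, total 41, null rate 5%, binomial counts. From Section 10.D(2): reject if the total is at least 5.

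**Formulas.**

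- Early stopping: PET = P(X1 ≤ 1 | 21, p)
- Rejection: Σ over x ≥ 2 of P(X1 = x | 21, p) × P(X2 ≥ 5 − x | 20, p)
- Expected sample size: EN = 21 + 20 × (1 − PET)

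**Reproducing Table 1.**

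| True rate | Early stop, exact (printed) | Rejection, exact (printed) | EN, exact (printed) |
|---|---|---|---|
| 5% | **71.7% (66%)** | **4.57% (6%)** | 26.66 (27) |
| 10% | 36.5% (36%) | 35.3% (35%) | 33.71 (34) |
| 15% | 15.5% (16%) | 70.8% (71%) | 37.90 (38) |
| 20% | 5.8% (6%) | 90.2% (90%) | 39.85 (40) |
| 25% | 1.9% (2%) | **97.25% (98%)** | 40.62 (41) |

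Every cell reproduces after rounding except the three in bold, so the method is the one behind the plan's table.

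**The 5% row in full.**

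- PET = 0.95^21 + 21 × 0.05 × 0.95^20 = 0.3406 + 0.3764 = 0.7170.
- Rejection, by number of stage-1 responses:
  - 2 responses: 0.19811 × 0.07548 = 0.01495
  - 3 responses: 0.06604 × 0.26416 = 0.01744
  - 4 responses: 0.01564 × 0.64151 = 0.01003
  - 5 or more: 0.00324 × 1 = 0.00324
  - The sum is 0.0457 after rounding.
- EN = 21 + 20 × 0.2830 = 26.66.

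**Checks against the plan's own figures.**

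1. Table 2 gives p = 0.2830 for 2 responses. This equals P(X1 ≥ 2 | 21, 0.05), the chance of continuing, so early stopping is 1 − 0.2830 = 71.7%.
2. A PET of 66% gives EN = 21 + 20 × 0.34 = 27.8, which rounds to 28. A printed value of 27 needs a PET between about 67.5% and 72.5%.
3. Table 2 gives p = 0.0460 at 5 responses, the rejection threshold. That matches 0.0457 and the stated 5% significance, but not 6%.

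**Could another rule give the printed values?** With 21 and 41 patients, rejecting at 4 or more gives 11.4% and at 6 or more gives 1.45%. A single-stage rule of 5 of 41 gives 5.25%. None is 6%. Early stopping of 66% needs n1 = 24 (66.1%), which gives an EN of 29.8. A search over two-stage designs at 5% significance and 90% power returns the plan's own design as the one with the smallest EN under the null, at 26.66.

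**Toxicity standard error.** SE = √(p(1 − p)/21) is 7.8% at p = 15%, 10.0% at 30%, 10.4% at 35% and at most 10.9% at 50%. The bound of less than 10% therefore fails for rates from 30% to 70%, which include the 35% that Section 6.A calls unacceptably high. The other precision claims hold: the widest Wilson 95% interval is 39.3% at n = 21 (claimed at most 40%) and 29.3% at n = 41 (claimed at most 32%), and the SE at n = 41 is at most 7.8% (claimed below 8%).

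**The case against.** The strongest reply is that nothing operational depends on these figures. The stopping bound, the rejection threshold, the 5% significance and the 90% power are all right. Both null-row errors understate the design: it stops an inactive regimen more often, and gives false positives less often, than printed. The correct significance level is already in the text and in Table 2, and the final decision follows the threshold of 5 rather than Table 1. All of this stands, and it makes the point a correction to reporting and not a fault in the design.

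The 98% is out by only 0.75 of a point, at a rate that is not the design alternative. The standard-error bound concerns a different endpoint, holds at the acceptable toxicity rate of 15%, and drives no decision, because toxicity stopping uses the Pocock boundary in Section 6.A. It is fair to treat both as minor, but both are still incorrect as written.

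The documents do not show how the 66% arose. P(at least 1 response in 21) at a 5% rate is 65.9%, which is also the Table 2 p-value for 1 response. A mix-up there is possible, but that is conjecture. The 66% appears in both text and table, so a conversion fault is unlikely. None of these replies defends the 66% or the 6% themselves.

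**Conclusion.** The concern holds. At a true rate of 5%, early stopping is 71.7% against 66% printed, a gap of 5.7 points, and the rejection probability is 4.57% against 6% in Table 1. The result rests only on the stated rule and the plan's own binomial assumption. The design does not exceed its 5% significance level; only the Table 1 cell says so. The minor items also hold: power at 25% is 97.25% against 98%, and the stage-1 standard error can reach 10.9% against a stated bound of 10%. The errors should be corrected because they are stated operating characteristics of the primary efficacy design. No enrolment, stopping, rejection or toxicity decision changes.

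**What to change.** - Section 10.C, text and Table 1: change the early-stopping probability at 5% from 66% to 72% (two places).
- Table 1, 5% row: change the power entry from 6% to 5%, or to 4.6% if one decimal is shown (one place).
- Section 10.C, text and Table 1: change the power at 25% from 98% to 97% (two places).
- Section 10.C, paragraph on toxicity precision: change the stage-1 standard-error bound from less than 10% to less than 11%, and keep the 40% interval-width statement (one place).

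That is six text edits. The sample sizes, stopping bound, rejection threshold, 5% significance, 90% power, expected sample sizes and analysis stay as they are. The corrected figures should be the ones carried into the detailed SAP.
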